Randomization: Subjects in each of the two age groups (5-17 and ≥ 18 years of age) will be randomized to either the dexamethasone or placebo group (0.3 mg/kg every 12 hours x 4 doses, then tapered). Randomization will be stratified by site, age group, and severity of ACS to preserve balance across treatment groups.

Title of the Protocol: Randomized Trial of Oral Dexamethasone for Acute Chest Syndrome

Data Analyses: We will evaluate the difference in duration of symptoms for ACS between the two treatment groups using a generalized linear mixed model (GLMM). Here, the natural log of the duration of symptoms will act as the dependent variable of interest and the treatment status as the grouping factor. As a secondary analysis, the duration of hospitalization, supplemental oxygen, and fever will be analyzed in a similar manner. Laboratory parameters will be analyzed using a GLMM model, with treatment group, baseline laboratory value, age group, severity, and site as fixed effects and subject as a random effect. Clinical endpoints and AEs will be summarized by treatment and analyzed for differences across treatment group. Two formal interim analyses will be performed on the primary efficacy variable. The first interim analysis will take place when 56 subjects have resolved signs and symptoms of ACS OR have been discharged from the hospital. In this interim analysis, the primary efficacy hypothesis will be tested at the $\alpha = 0.001$ level. The study will be stopped if significant efficacy is identified. The second interim analysis will be performed when 112 subjects have resolved signs and symptoms of ACS OR have been discharged from the hospital. The primary efficacy hypothesis will be tested at the $\alpha = 0.01$ level. If significant efficacy is identified for total subjects and for children, the study will be stopped. Otherwise, the study will continue enrollment to 112 children, after which the primary efficacy hypothesis will be tested on the $\alpha = 0.039$ level.

Human Subjects: Potential risks include avascular necrosis, vaso-occlusive crisis, mood changes, hypertension, nausea, vomiting, dyspepsia, gastric ulceration, delayed wound healing, acne, and infection.

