7.1.2 Description of Type of Study

This is a multi-center, randomized, double-blind, placebo-controlled Phase III clinical trial that will include at least 56 subjects with SCD who are hospitalized for ACS. Individuals who meet entry criteria will be randomized to receive either dexamethasone or placebo. Dexamethasone will be administered initially as 0.3 mg/kg by mouth every 12 hours for a maximum of 4 doses (2 days) or until discharge from the hospital, whichever occurs first. Afterward, the study drug will be tapered over 6 days for a total duration of therapy not to exceed 8 days. Due to possible age-related and ACS severity-related differences in the duration of signs and symptoms of ACS, randomization will be stratified by age and severity of ACS (see Section 8.3). We are enrolling a maximum of 112 pediatric subjects. We will enroll adult subjects at the rate site participation will allow, which we anticipate will be no more than 56 subjects. Interim analyses will be performed when a total of 56 subjects and 112 subjects have completed their hospital stay. If we do not stop enrollment after these interim analyses are completed, we will continue to enroll up to a maximum total of 112 pediatric subjects. The efficacy and safety of dexamethasone will be compared to placebo in the context of standard supportive care for ACS.

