9.2 Randomization and Masking

After enrollment, subjects will be randomized to one of two treatment arms. Subjects in Arm 1 will receive oral dexamethasone. Subjects in Arm 2 will receive oral placebo. A computer-generated, adaptive randomization schema will be used to allocate subjects 1:1 between the two treatment arms. Randomization will be stratified by site, age and the severity of ACS (see Section 8.3). In order to increase the likelihood of balance in treatment allocations, subjects will be randomized using the standardized range variation (79) of the sequential allocation algorithm of Pocock and Simon (80), a minimization method. This method attempts to achieve treatment balance on several subject characteristics (i.e. age group, site, and severity of ACS in this study) simultaneously – not within separate strata. Minimization consists of biasing the treatment allocation so as to minimize the total imbalance between the treatment groups on some scale (81). The order of entry of the subjects to the various centers and in the various prognostic groups is assumed to be random. As minimization is a dynamic method that uses information on subjects already entered to allocate treatment to the next subject, a continuous updating of the information related to previous treatment allocations is required, thus a centralized randomization system will be used.

Pharmacists at each center will be unblinded and will utilize information from the interactive voice/web randomization system (IVRS) at the SDMC to obtain a new treatment assignment for a subject and provide each subject with appropriate dosing of both therapies. The IVRS system has the capability of providing unblinding information in case of a medical emergency where the exact study drug is needed in order to appropriately treat a subject.

The time interval between Randomization and the first dose of study drug administration will be no longer than 2 hours. In the event a subject's first dose occurs outside the 2-hour time limit, the subject will still be included in the study and the analysis. This is in the spirit of the intention-to-treat analysis. The amount of time in excess of the 2-hour limit until the first dose of study drug will also be recorded. This event will be documented as a protocol deviation.

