11.6.3 Safety Alerts

Three months after the first subject is enrolled in the study, and at the end of each 3-month period thereafter, if any SAEs (expected or unexpected) have been reported in the study during the preceding 3 months, the SDMC will:

- Use the current version of the MedDRA dictionary to code all AEs (serious or not) that have been recorded on study AE forms.
- Make a “snapshot” copy of the AE data, including MedDRA codes.
- Create frequency tables of treatment x occurrence (yes or no, since inception of the study) of all subjects. One table will be created for each highest level MedDRA term for which SAEs have been reported. The counting units are subjects, not events.
- Compute Fisher’s Exact Test (FET) statistic to test the alternative hypothesis that occurrence of SAEs is not independent of treatment group. The FET p-value is not adjusted for multiplicity.
- If the FET p-value is less than the critical value shown in Table 11.3 and the active treatment group has a higher AE rate, the SDMC will conduct further statistical analyses as indicated by the circumstances and report the results to the Chair of the DSMB subcommittee monitoring this study, the PI, and the NHLBI Project Officer.

The SDMC will not file a report of all SAEs if none of the FET p-values is less than the critical value shown in Table 11.4 or if the relative risk is less than 1.

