13.2.3 Safety Analyses

Safety analyses will be performed on all randomized and dosed subjects (i.e., the ITT population). An analysis of safety will include a summary of AEs, SAEs, vital signs, clinical laboratory tests (CBC and reticulocyte count), physical examination, urine output and daily fluid balance, blood culture, peripheral oxygen saturation, and baseline and interim history. All safety outcomes will be summarized by treatment, age strata, and measurement time point (if appropriate).

Treatment-emergent AEs, drug-related AEs, SAEs, and drug-related SAEs (as determined by the investigator) will be classified using the Medical Dictionary for Regulatory Activities (MedDRA, Version 6.0 or later) preferred terms. A treatment-emergent AE is one that started or worsened in severity after initial administration of study drug. All treatment-emergent AEs and SAEs will be classified with regard to severity and duration of the event. These data will be summarized by treatment group, age strata, body system, and preferred terms within a body system. AE comparisons across treatment groups, stratifying on age group, will be made using a Chi-square test on any AEs that occur in more than 10% of the subjects. Each occurrence of an AE (classified on the basis of MedDRA terminology) will be reported separately for a given subject.

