- the Type I error rate is 0.05,
- and the power is 90%,

then the necessary amount of subjects needed per treatment group is 54. We do not anticipate many dropouts prior to the assessment of the primary endpoint because the population should remain in the hospital under observation until that time. However, we will add two more subjects to each treatment arm to compensate for potential withdrawals, so the total number of subjects needed per treatment group is 56.

We have also explored alternative scenarios and concluded that 56 subjects per treatment group is sufficient under the following conditions:

- the lognormal population standard deviation for the placebo group ≤ 0.6 (and thus follows the Bernini⁴⁷ study), and
- the lognormal population standard deviation of the dexamethasone group ≤ 0.5 (and thus is in the range of both the Bernini and Huh study), and
- the lognormal mean of the placebo group is 4.0, 4.1, 4.2, or 4.3, and

- the lognormal mean of the dexamethasone group is 3.6, 3.7, 3.8, 3.9, or 4.0, and
- the mean difference in LOS between the two treatment groups is ≥ 30 hours.

If we wish to vary assumptions, we would see differences in the number of subjects needed.

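### The final safety analysis tests only AEs above 10% incidence; read as pooled incidence, this leaves a split as extreme as 11 v 0 at 112 subjects tabulated but untested

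*Protocol*

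**What the plan says.** Section 13.2.3 first has all treatment-emergent AEs and SAEs tabulated, with no frequency limit: "These data will be summarized by treatment group, age strata, body system, and preferred terms within a body system". It then restricts the between-arm test, stratified by age group, to a "Chi-square test on any AEs that occur in more than 10% of the subjects". It does not say whether the 10% refers to both arms together or to one arm.

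The synopsis lists the harms expected of the drug: "Potential risks include avascular necrosis, vaso-occlusive crisis, mood changes, hypertension, nausea, vomiting, dyspepsia, gastric ulceration, delayed wound healing, acne, and infection".

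Section 11.6 sets up separate monitoring tests. For SAEs, each quarter, the coordinating center is to "Compute Fisher’s Exact Test (FET) statistic to test the alternative hypothesis that occurrence of SAEs is not independent of treatment group" (Section 11.6.3). Section 11.6.4 does the same for all AEs every six months. Both count subjects cumulatively, work per highest-level MedDRA term and have no frequency threshold. Table 11.4 sets the alert at p<0.01 with the higher rate on active treatment.

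The denominators come from three places. Section 9.2 says an "adaptive randomization schema will be used to allocate subjects 1:1 between the two treatment arms". Section 13.4 concludes that "the total number of subjects needed per treatment group is 56". Section 7.1.2 states "We are enrolling a maximum of 112 pediatric subjects" and describes adult enrollment as a number "which we anticipate will be no more than 56 subjects".

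**The concern.** The rule chooses which AEs to compare by how common they are overall. A harm caused by the drug falls mainly in one arm, so its pooled rate is about half its rate on dexamethasone. The more one-sided the harm, the more the pooled rate understates it. The screen therefore works against the pattern a safety comparison should detect, while an AE equally common in both arms passes easily.

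At stake is whether the final report attaches any measure of evidence to a clear preferred-term excess on dexamethasone. Section 5 gives defining potential toxicities as one reason for further study.

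**Working it through.** **Denominator.** Section 13.4 assumes log-scale SDs of 0.6 and 0.3, log means of 4.25 and 3.95, two-sided alpha 0.05 and 90% power.
- Normal approximation: n = (0.6² + 0.3²)(1.96 + 1.2816)² / 0.30² = 52.5, so 53 per arm.
- Satterthwaite t-test (noncentral t): power 0.895 at 53 and 0.901 at 54.

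The plan's 54 per group is reproduced. Two more per arm for withdrawals gives 56 per arm, N=112. The anticipated maximum is 112 children + 56 adults = 168, or 84 per arm if balanced. The first interim look is at 56 subjects, or 28 per arm.

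**What the pooled rule demands.** With equal arms, pooled rate = (rate on dexamethasone + rate on placebo)/2. If the placebo rate is 0, a pooled rate above 10% requires more than 20% on dexamethasone.

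**Largest untested counts.** An AE is untested when its total does not exceed 10% of N. All p-values are two-sided Fisher.

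| N | 10% of N | Largest untested total | Split | p |
|---|---|---|---|---|
| 56 | 5.6 | 5 (8.9%) | 5 v 0 | 0.051 |
| 112 | 11.2 | 11 (9.8%) | 11 v 0 | 0.0006 |
| 112 | 11.2 | 11 (9.8%) | 10 v 1 | 0.008 |
| 112 | 11.2 | 11 (9.8%) | 9 v 2 | 0.053 |
| 168 | 16.8 | 16 (9.5%) | 16 v 0 | 0.00001 |

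At N=112, 11 v 0 is 19.6% against 0%. At N=56, an uncorrected chi-square for 5 v 0 gives p=0.019, but counts that small call for an exact test.

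**How often it bites.** The documents give no AE incidences, so the true rates below are assumptions spanning a range. I enumerated both binomials exactly at 56 per arm. A significant excess means Fisher p<0.05 with dexamethasone higher.

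| Assumed placebo v dexamethasone | P(untested) | P(significant excess) | P(both) | Share of significant excesses untested |
|---|---|---|---|---|
| 1% v 15% | 0.822 | 0.724 | 0.551 | 76% |
| 5% v 15% | 0.554 | 0.293 | 0.109 | 37% |
| 5% v 20% | 0.236 | 0.582 | 0.083 | 14% |

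**Whether monitoring fills the gap.** If 11 v 0 were the only events in a highest-level term, p=0.0006 is below 0.01 and an alert follows. Unrelated events in the same term dilute it. With 2 added per arm (13 v 2) p=0.004, still an alert. With 4 added (15 v 4) p=0.0104, and with 5 added (16 v 5) p=0.014; neither alerts.

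**Threshold applied to either arm.** At 56 per arm, 10% is 5.6, so an AE is untested only if neither arm has more than 5 cases. The most extreme such split, 5 v 0, gives p=0.057, so no Fisher-significant excess is screened out. At 84 per arm, 10% is 8.4, and 8 v 0 (p=0.007) would still be untested.

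**The case against.** The strongest reply is that the protocol does compare rarer AEs. A reader might infer from the rule that arms are compared only above 10% anywhere in the trial. That is wrong: Sections 11.6.3 and 11.6.4 test SAEs and all AEs with no frequency threshold, and an isolated 11 v 0 would alert the DSMB. This limits the point to the final analysis. It does not remove it, because those tests work at the coarsest MedDRA level and serve monitoring.

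A reader might also infer that an excess would be hidden. It would not: Section 13.2.3 tabulates every AE by arm, and Section 13.3.3 makes all non-primary p-values descriptive, so no formal decision turns on the missing test.

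Nor do the documents show that the named steroid risks would be the ones missed. They give no incidences. Table 11.3 lists most of these risks as sickle-cell-related, so placebo cases are plausible, and higher placebo rates shrink the loss, as the 5% rows show. Rebound vaso-occlusive crisis has its own tests (Sections 11.6.6 and 13.2.2).

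The denominator is also open. If the 10% is read per arm, 11 v 0 at N=112 is tested. The pooled reading is the plainer one, but the text does not settle it.

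Finally, a list of AEs of special interest commonly belongs in the SAP, so its absence here is no fault. The fault lies in the stated screening rule.

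**Conclusion.** The point holds for the final safety analysis in Section 13.2.3, on the pooled reading and with equal arms. There, an AE absent on placebo is compared only if it exceeds 20% on dexamethasone. Splits up to 11 v 0 at N=112 and 16 v 0 at N=168 are shown but not tested. If the trial stops at 56 subjects, no Fisher-significant split is lost.

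The 11 v 0 and 16 v 0 limits are arithmetic from the protocol's own figures. The 76%, 37% and 14% shares rest on assumed rates and show how strongly the loss depends on the placebo rate. The monitoring tests are a partial safeguard. The rule is worth correcting because it screens out one-sided harms, but it does not conceal data and does not affect the primary analysis.

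**What to change.** In Section 13.2.3:

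- (a) State the threshold as more than 10% of subjects in either treatment group. This settles the denominator. At 56 per arm it leaves no Fisher-significant excess untested, and it also covers harms nobody anticipated.
- (b) For the steroid risks named in the synopsis, report the risk difference with an exact 95% CI and Fisher's exact test whatever their frequency, counting each subject once. This covers the named risks in the remaining gap at 84 per arm, where (a) alone would still miss 8 v 0.

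The cost is one short table and some additional p-values, already descriptive under Section 13.3.3. Alpha for the primary hypothesis, data collection and treatment rules are unchanged.

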13.2.4 Interim Analyses

Two formal interim analyses will be performed on the primary efficacy variable. The first interim analysis will take place when 56 subjects have resolved signs and symptoms of ACS *or* have been discharged from the hospital. To test for differences between the treatment arms, the same F-test from the GLMM specified in the primary analysis will be used with a Peto stopping boundary of $p < 0.001$.⁷⁸ The study will be stopped if significant efficacy is identified. The second interim analysis will be performed when 112 subjects have resolved signs and symptoms of ACS *or* have been discharged from the hospital. The primary efficacy hypothesis will be tested at the $\alpha = 0.01$ level on the total subjects,

and the 0.05 level for the children. If significant efficacy will be identified for total subjects and for children, the study will be stopped. Otherwise, the study will continue enrollment to 112 children, after which the primary efficacy hypothesis will be tested on the $\alpha = 0.039$ level. By utilizing these alpha levels for each test and a step-down procedure for the pediatric sub-population, the overall study alpha level for the test of the primary hypothesis remains at the 0.05 level.

In order to ensure that future subjects are not exposed to study drug unnecessarily, the DSMB will also be provided with the conditional probability of completing a successful trial at the interim analyses under three scenarios: (1) the treatment difference continues to be the same as in the first portion of the trial; (2) the treatment difference is zero for the next portion of the trial; (3) the treatment difference is 30 hours for the next portion of the trial. Based on this information, the DSMB can make an informed decision about the futility of the trial.

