Nevertheless, dexamethasone is the first treatment shown to benefit patients with ACS in randomized, placebo-controlled trials.^{47, 48} But the generalizability of these trials is limited, given that sample sizes were small, only children were studied, and individuals with severe ACS were few. The rebound effect is also worrisome. In addition, the statistical analysis and interpretation of the results was clouded because the observations were not all independent—some children with multiple episodes of ACS were included more than once in the trial.

Thus, further study of this promising treatment in a broad population is needed to clearly define its benefits and potential toxicities. This study aims to determine whether a tapered regimen of dexamethasone can both be effective and eliminate rebound VOC. The taper will follow 4 doses of the study drug as specified in the Bernini study,⁴⁷

because simply extending the duration of (un-tapered) dexamethasone to 6 doses, as in the Huh study,⁴⁸ did not prevent rebound attacks. Both adults and children who have ACS of any severity will be studied, dose modifications for marked leukocytosis will be incorporated, and individuals will participate only once. This study will also measure differences in pulmonary function at a 1-month follow-up visit, and a panel of biomarkers will be obtained at several time points during the course of study drug treatment.

Rationale for Biomarker Assessment in ACS:

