10.3.3 Follow-up Studies

The required measurements and studies at the Follow-up clinic visits are an ACS assessment, CBC, reticulocyte count, oxygen saturation by pulse oximetry, vital signs (includes blood pressure monitoring), and a pain assessment. At each visit, a standardized interval history for pain intensity, pain treatment, and respiratory symptoms will be obtained, as well as any inpatient or outpatient evaluation and management of SCD-related complications which includes the collection of any transfusions the subject received, and an assessment of compliance with the home medications will be completed. AEs occurring after discharge will be captured, especially events requiring hospitalization. **Any additional hospitalizations in the 1 week after discharge for**

VOC will be counted as “rebound VOC” hospitalizations. Additionally, the following will be obtained at the 1-month follow-up only: physical examination, a chest radiograph (PA and lateral views) and pulmonary function testing (PFT) without methacholine challenge or bronchodilators. PFTs will include measurement of forced vital capacity (FVC), forced expiratory volume in 1 second (FEV₁), average forced expiratory flow between 25 and 75% of expired vital capacity (FEF_{25-75%}), and peak expiratory flow rate (PEFR). Also, the flow-volume loop will be recorded and the FEV₁/FVC will be calculated.

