Rehospitalization after Acute Chest Syndrome (“rebound”) is a significant safety concern with this study. The current study has been designed to monitor this concern every three months (quarterly) after the first subject has been enrolled. Specifically, the percent of subjects with a rehospitalization would be compared between the two treatment groups and if the Dexamethasone arm had a significantly higher percentage than the placebo arm, the DSMB would be alerted immediately to review the data in detail and decide whether the difference warranted a change to the study or stopping the study. Please note that this is similar to the comparisons made on other safety measures, such as serious adverse events and all adverse events. It is not clear, however, how often these suspension guidelines would be invoked under different rates of rebound. The purpose of this appendix is to describe the characteristics of the suspension guidelines in terms of probability of stopping early under different assumed rates of rebound for each treatment arm.

Previous studies (Huh (XXXX) and Bernini (XXXX)) found that treatment with Dexamethasone increased the percentage of subjects with rebound by a factor of six. Specifically, the Bernini study found that 5% of subjects treated with only standard of care (placebo arm) had a rehospitalization, while 27% of subject treated with Dexamethasone had a rehospitalization. Similarly, the Huh study found 6% in the placebo arm and 31% in the Dexamethasone arm had rehospitalizations. The tapering dosing schedule specified in this study is expected to reduce the number of rebounds in the Dexamethasone arm, so we wish to look at a range of percentages for the Dexamethasone arm and assume 5% of the placebo subjects have a rebound. The following table presents five “scenarios” that could be reasonably expected to be observed in the trial.

Table X. Assumed percentage of rebounds for each scenario considered.

Scenario	% Rebound		Expected total number of rebounds
	Placebo	Dexamethasone	
A	5%	25%	17
B	5%	30%	20
C	5%	10%	8
D	5%	5%	6
E	5%	2.5%	4

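### The efficacy stop is mandatory on the duration test alone and is not linked to the rebound data, which matters mainly at the first interim look

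*Protocol*

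**What the plan says.** **Stopping rule.** Section 13.2.4 plans two efficacy looks. On timing it says: "The first interim analysis will take place when 56 subjects have resolved signs and symptoms of ACS", or have been discharged; section 7.1.2 puts it as "Interim analyses will be performed when a total of 56 subjects and 112 subjects have completed their hospital stay". The boundary at the first look is p < 0.001 on the primary analysis, and the consequence is "The study will be stopped if significant efficacy is identified". At 112 subjects the test is at 0.01 for all subjects and 0.05 for children: "If significant efficacy will be identified for total subjects and for children, the study will be stopped". The synopsis repeats both stops. The only further interim information that 13.2.4 assigns to the DSMB is conditional power, for judging futility.

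**Rebound.** Section 5 states: "This study aims to determine whether a tapered regimen of dexamethasone can both be effective and eliminate rebound VOC". Section 6.2 makes prevention of rebound a secondary objective. Section 10.3.3 defines a rebound event as "Any additional hospitalizations in the 1 week after discharge for" VOC. Appendix 2 calls rebound a significant safety concern and says the earlier trials found that dexamethasone "increased the percentage of subjects with rebound by a factor of six", quoting 5% v 27% and 6% v 31%.

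**Parallel monitoring.** Section 11.6.6 has the data center compare rebound by arm every three months and alert the DSMB if Fisher's exact p is below 0.025 with dexamethasone worse. The paragraph after that list says the reverse: that no report is filed when p is below 0.025. Section 11.9.1 gives the DSMB a six-monthly safety review, and section 14.1 lets it recommend stopping for safety at any time.

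**The concern.** The efficacy stop is written as automatic, and its trigger looks only at the index episode. By section 7.1.1 the primary endpoint is the shorter of symptom duration and hospital stay. If dexamethasone shortened the index stay but moved some illness to the week after discharge, the primary test would record the gain and not the cost.

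The rebound monitoring runs beside this rule and can prompt a safety stop. It has no stated route to delay or override an efficacy stop. A crossing at 56 subjects would therefore end enrollment with about 28 per arm for the rebound question, half of the 56 per arm that the sample size section plans. The trial could then report efficacy while leaving open the other half of its stated aim.

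**Working it through.** **1. Reproducing the plan's sample size.** Inputs from section 13.4: log means 4.25 and 3.95 (difference 0.30), log SDs 0.6 (placebo) and 0.3 (dexamethasone), two-sided 0.05, Satterthwaite t-test, equal arms.

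- SE = sqrt((0.6² + 0.3²)/n) = sqrt(0.45/n); noncentrality = 0.30/SE.
- df = (n − 1)(0.36 + 0.09)²/(0.36² + 0.09²) = 1.47(n − 1).
- At n = 54: SE = 0.0913, noncentrality 3.29, power 90.07%. At n = 53: 89.5%. The plan's 54 per arm is reproduced.

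**2. Chance of stopping at the first look.** Same formula, n = 28 per arm, two-sided 0.001.

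- Planning values: SE = sqrt(0.45/28) = 0.127, noncentrality 2.37, power **14%**.
- 1998 trial (Table 13.2: 4.217 and 3.795; SDs 0.574 and 0.331): difference 0.422, SE = 0.125, noncentrality 3.37, power **45%**.
- Follow-up trial (Table 13.2: 4.216 and 3.954; SDs 0.707 and 0.560): difference 0.262, SE = 0.170, noncentrality 1.54, power **3%**.

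**3. What the rebound alert can see.** Placebo rate 5% (Appendix 2). The probability is the exact sum over two binomials of outcomes with two-sided Fisher p < 0.025 and dexamethasone worse, for a single look:

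| True dexamethasone rate | 28 per arm | 56 per arm |
|---|---|---|
| 10% | 1.5% | 4% |
| 20% | 19% | 48% |
| 25% | 35% | 74% |
| 30% | 53% | 90% |

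Adding earlier quarterly looks raises the 25% and 30% entries at 28 per arm only to about 38% and 55% (simulation, 4,000 trials).

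In counts at 28 per arm: 7 v 1 rebounds gives p = 0.051 and no alert; 8 v 1 gives p = 0.0248 and an alert. A split of 4 v 1 is a difference of 10.7 points, 95% CI −5.8 to 28.2 (Newcombe).

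**4. Both events together.** Treating the efficacy crossing and the missed alert as independent (an assumption), with miss probabilities 1 − 0.526 = 47% and 1 − 0.354 = 65%:

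- planning values: 0.140 × 0.47 to 0.65 = about 7% to 9%;
- 1998 trial: 0.448 × 0.47 to 0.65 = about 21% to 29%;
- follow-up trial: 0.033 × 0.47 to 0.65 = about 1.5% to 2%.

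**5. Rebound windows still open at the data cut.** Appendix 2 accrual: 112 subjects in 15 months = 112/(15 × 30.44) = 0.245 per day. Over 7 to 9 days that is 1.7 to 2.2 subjects, about 2 of 56. At half or double that accrual, 7 days gives about 0.9 to 3.4.

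**The case against.** Rebound is not ignored. It is tested by arm every three months, a rebound admission is also a serious adverse event reportable within a day, and the DSMB may weigh a split such as 7 v 1 in its safety review whether or not an alert fires. In practice a DSMB would look at rebound before endorsing an efficacy stop. This stands as far as it goes, and it is why the point is not that the harm goes unwatched. But the text gives the monitoring no bearing on the efficacy stop, and section 11.6.6 as written contradicts its own alert. Appendix 2's reassuring figures (94% at 5% v 30%, 68% at 5% v 25%) describe a chi-square test at 0.05 with looks up to 88 subjects, not the Fisher rule at 56.

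A reader might infer that the main fault is timing, since the trigger precedes the end of the one-week window. The documents do not support that weight. About 2 of 56 subjects are affected, nothing ends their follow-up when enrollment stops, visits run to 30 days after discharge, and section 12.2 takes the DSMB data snapshot about a month before each meeting.

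A reader might also extend the low-precision argument to the second look. At 112 subjects the alert has 74% to 90% probability at 5% v 25% to 30%, and 56 per arm is the planned size. The mandatory wording recurs there; the thin rebound data do not.

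Finally, the 25% to 30% rates come from untapered regimens, and Appendix 2 expects the taper to lower them. That is fair, but smaller excesses are harder still to detect at 28 per arm.

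**Conclusion.** The concern holds in a limited form. The efficacy stop is mandatory, rests on the duration test alone, and is unconnected to the rebound comparison. At the first look this could end enrollment when the alert has a 35% to 53% chance of firing at rates near those of the earlier trials. The chance of reaching that point is modest: 14% to stop at the first look under the planning values, and roughly 7% to 9% to stop and also miss the alert. Reading this as a defect that must be cured before the trial can proceed would go too far, because the parallel monitoring exists and a DSMB can use it. It is a clear, inexpensive improvement.

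Assumptions: hospital stay stands in for the primary endpoint, as section 13.4 does; an unadjusted Satterthwaite test stands in for the covariate-adjusted model; 28 and 56 per arm; placebo rebound 5%; independence for the joint figures; Appendix 2 accrual.

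**What to change.** 1. In section 13.2.4 and the synopsis, at both looks, replace the mandatory stop. If the boundary is crossed, the DSMB may recommend stopping for efficacy after it has reviewed rebound hospitalizations by arm (subjects with an event, difference with 95% CI) for the interim subjects, with the one-week post-discharge window complete.
2. State that the efficacy boundary is non-binding. This cannot raise the type I error: the error is bounded by the null probability that any of the planned tests crosses, and declining to stop adds no test.
3. In section 11.6.6, correct the non-reporting sentence so that it agrees with the alert bullet above it.

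The essential change is the non-binding boundary with DSMB review of rebound. Waiting for windows to close would not resolve the harm by itself, because the comparison stays at 28 per arm. No fixed rebound threshold is proposed; at that size even 4 v 1 has an interval from −5.8 to 28.2 points, so judgement is needed.

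Cost: protocol, SAP and DSMB charter wording, and about one to two weeks' delay per interim. The real downside is that some subjects may be randomized to placebo after a boundary has been crossed.
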